#### 8.2.1. Physical Examinations

- A complete physical examination will include, at a minimum, assessments of the cardiovascular, respiratory, gastrointestinal, and neurological systems. It will be performed at Screening, Check-in for each period, and at the EOS or upon ET. Height, BMI (at Screening only) and weight will also be measured and recorded as outlined in the SOA (Table 1).
- A symptom-driven physical examination may be performed at other times, at the study physician's discretion.

• Investigators should pay special attention to clinical signs related to previous serious illnesses.

#### 8.2.2. Vital Signs

- Oral temperature, pulse rate, respiratory rate, and systolic and diastolic blood pressure (mm Hg) will be assessed.
- Routine blood pressure and pulse measurements will be assessed with a completely automated device. Manual techniques should be used if repeat measurements are necessary due to abnormal results.
- Blood pressure and pulse measurements should be preceded by at least 5 minutes of rest for the participant in a quiet setting without distractions (eg, television, cell phones). Ideally, the same arm for each participant should be used for measurements.

## 8.2.3. Vital signs will be measured in a semi-supine position after 5 minutes rest. Electrocardiograms

• Participants will be resting in the supine position for at least 15 minutes prior to and 5 minutes after each nominal time point for ECG extraction. Triplicate 12-lead ECG will be conducted as outlined in the SoA (see Table 1) to obtain heart rate, PR, QRS, QT, and QTc intervals. Heart rate and interval data will be recorded in the eCRF. QT corrected for heart rate using Fridericia's formula should be recorded as the QTc reading (unless unavailable and then QTcB may be recorded). Refer to Section 7 for QTc withdrawal criteria and any additional QTc readings that may be necessary.

#### 8.2.4. Clinical Safety Laboratory Assessments

- See Section 10.2 for the list of clinical laboratory tests to be performed and the SoA (Table 1) for the timing and frequency.
- The Investigator must review the laboratory report, document this review, and record any clinically relevant changes occurring during the study in the AE section of the CRF. At the Investigator's discretion, all abnormal values may be repeated to confirm results. The laboratory reports must be filed with the source documents.
- All laboratory tests with values considered clinically significantly abnormal during participation in the study after the last dose of the study intervention should be repeated until the values return to normal or baseline or are no longer considered clinically significant by the Investigator or Medical Monitor.
  - If such values do not return to normal/baseline within a period of time judged reasonable by the Investigator, the etiology should be identified, and Alexion notified.
  - All protocol required laboratory assessments, as defined in Section10.2, must be conducted in accordance with the laboratory manual and the SoA (Table 1).
  - All laboratory values from nonprotocol specified laboratory assessments also must be recorded in the CRF.

#### 8.2.5. Suicidal Ideation and Behavior Risk Monitoring

Not applicable.

#### 8.2.6. Pregnancy

- Pregnancy data from female participants and female spouses/partners of male participants will be collected from the first dose of the study intervention through 90 days post the last dose and at the time points specified in the SoA. Any female participant who becomes pregnant while participating in the study will be discontinued from the study intervention. If a pregnancy is reported, the Investigator must immediately inform Alexion within 24 hours of awareness of the pregnancy and follow the procedures outlined in Section 10.4.
- For all Alexion products, both in development or post approval, exposure during pregnancy must be recorded and the pregnancy followed until the outcome of the pregnancy is known (ie, spontaneous miscarriage, elective termination, normal birth, or congenital abnormality), even if the participant discontinues study intervention or withdraws from the study. The corresponding infant must be followed for 3 months postpartum.
- Pregnancy is not considered an AE (Section 10.4) unless there is a suspicion that the study intervention may have interfered with the effectiveness of a contraceptive medication. However, complications of pregnancy and abnormal outcomes of pregnancy are AEs and may meet the criteria for a SAE (eg, ectopic pregnancy, spontaneous abortion, intrauterine fetal demise, neonatal death, or congenital anomaly) (Section 8.3). Elective abortions without complications should not be reported as AEs.

## 8.3. Adverse Events and Serious Adverse Events

The definitions of AEs and SAEs can be found in Section 10.3.

Adverse events will be reported to the Investigator or qualified designee by the participant (or, when appropriate, by a caregiver, surrogate, or the participant's legally authorized representative).

The Investigator and any qualified designees are responsible for detecting, documenting, and recording events that meet the definition of an AE or SAE and remain responsible for following up AEs that are serious, considered related to the study intervention or study procedures, or that caused the participant to discontinue the study (see Section 7).

Procedures for recording, evaluating, follow-up, and reporting AEs and SAEs are outlined in Section 10.3.

## 8.3.1. Time Period and Frequency for Collecting Adverse Event and Serious Adverse Event Information

All AEs will be collected from the signing of the ICF until the EOS or ET Visit.

All SAEs will be recorded and reported to Alexion or the designee immediately and under no circumstance should this exceed 24 hours, as indicated in Section 10.3. The Investigator will submit any updated SAE data to Alexion within 24 hours of it being available.

Investigators are not obligated to actively seek AEs or SAEs after conclusion of the study participation. However, if the Investigator learns of any SAE, including a death, at any time after a participant has exited the study, and he/she considers the event to be reasonably related to the study intervention, the Investigator must promptly notify Alexion.

### 8.3.2. Method of Detecting AEs and SAEs

The method of recording, evaluating, and assessing causality of AEs and SAEs and the procedures for completing and transmitting SAE reports are provided in Section 10.3.

Care will be taken not to introduce bias when detecting AEs and/or SAEs. Open-ended and non-leading verbal questioning of the participant is the preferred method to inquire about AE occurrences.

#### 8.3.3. Follow-up of AEs and SAEs

After the initial AE/SAE report, the Investigator is required to proactively follow-up with each participant at subsequent visits/contacts. All SAEs will be followed until resolution, stabilization, the event is otherwise explained, or the participant is lost to follow-up (as defined in Section 7.3). Further information on follow-up procedures is provided in Section 10.3.

#### 8.3.4. Regulatory Reporting Requirements for SAEs

- Prompt notification by the Investigator to Alexion of an SAE is essential so that legal obligations and ethical responsibilities towards the safety of participants and the safety of a study intervention under clinical investigation are met.
- Alexion has a legal responsibility to notify both the local regulatory authority and other regulatory agencies about the safety of a study intervention under clinical investigation. Alexion will comply with country-specific regulatory requirements relating to safety reporting to the regulatory authority, Institutional Review Boards (IRBs)/Independent Ethics Committees (IECs), and Investigators.
- Suspected unexpected serious adverse reactions (SUSARs) must be reported according to local regulatory requirements and Alexion policy and forwarded to Investigators as necessary.
- An Investigator who receives an Investigator Safety Report describing an SAE or other specific safety information (eg, summary or listing of SAEs) from Alexion will review and then file it along with the IB and will notify the IRB/IEC, if appropriate according to local requirements.

#### 8.3.5. Adverse Events of Special Interest

There are no adverse events of special interest for this study.

#### 8.3.6. Retained and Biobanked Sample

A single biobanked serum sample will be collected pre-dose to serve as a retained safety sample during the study. At the end of the study, pre-dose safety samples will be biobanked to support assay development and determination of normal Cu and Mo levels in healthy participants. Samples may be stored and used for up to 5 years following completion of the study.

#### 8.4. Treatment of Overdose

For this study, any dose of ALXN1840 or celecoxib greater than that specified in the protocol will be considered an overdose.

Alexion does not recommend specific treatment for an overdose.

Overdoses are medication errors that are not considered AEs unless there is an untoward medical occurrence resulting from the overdose.

In the event of an overdose or suspected overdose, the Investigator or treating physician should:

- Contact the Medical Monitor immediately.
- Closely monitor the participant for any AE/SAE.
- Obtain a plasma sample for PK analysis if requested by the Medical Monitor (determined on a case-by-case basis).
- Document the quantity of the excess dose as well as the duration of the overdose in the CRF.

Decisions regarding dose interruptions or modifications will be made by the Investigator in consultation with the Medical Monitor based on the clinical evaluation of the participant.

### 8.5. Pharmacokinetics

- Whole blood samples will be collected for the measurement of plasma concentrations of total Mo and celecoxib as specified in the SoA (Table 1). Additional samples may be collected at additional time points during the study if warranted and agreed upon between the Investigator and Alexion. Collection of samples for PK evaluation should occur as close as possible to the scheduled time and actual time of collection should be documented on the eCRF. Samples collected within ± 10% of the scheduled time, or 30 minutes whichever is larger, will not be considered a protocol deviation. In the event of a safety occurrence and after agreement between the Investigator and Medical Monitor, up to 3 additional PK sampling timepoints may be added.
- Instructions for the collection and handling of biological samples will be provided by Alexion. The actual date and time (24-hour clock time) of each sample will be recorded.
- Samples will be used to evaluate the effect of ALXN1840 on the PK of celecoxib. Samples collected for analyses of plasma concentrations may also be used to evaluate safety or efficacy aspects related to concerns arising during or after the study.

• Excess/additional samples may be stored for up to 5 years and used for pharmacodynamic (PD) development and research to understand the pathways associated with the mechanism of action of ALXN1840; however, samples will not be used for genetic analyses (ie RNA or DNA analyses).

### 8.6. Pharmacodynamics

Plasma samples collected for PK may be used for analyzing the PD of ALXN1840 including, but not limited to plasma total Cu, ceruloplasmin (Cp), Cp-bound Cu (CpC), and potentially toxic Cu measured as labile-bound Cu (LBC) and PUF Cu and/or assessed via NCC/NCCcorrected.

### 8.7. Genetics

Blood samples for genetic testing of CYP2C9 polymorphism will be collected at clinical Check-in (Day -1). This study proposes to collect genetic polymorphism data to characterize potential impact of ALXN1840 on phenotypic CYP2C9 metabolism of celecoxib and evaluate the potential effect of genetic polymorphism on the between-participant variability of celecoxib PK. As this is an exploratory assessment, the study will not specifically select target participants with a certain proportion of CYP2C9 genotypes.

### 8.8. Biomarkers

Biomarkers are not evaluated in this study.

## 8.9. Immunogenicity

Not applicable.

## 8.10. Health Economics and Medical Resource Utilization

Health economic and medical resource utilization parameters are not evaluated in this study.

## 9. STATISTICAL CONSIDERATIONS

## 9.1. Statistical Hypotheses

The primary objective is to determine the effect of ALXN1840 on the PK of celecoxib. There is no formal null hypothesis to be statistically tested and used to drive declaration of study success or failure.

To assure the study has enough participants, to estimate the inhibitory effect of ALXN1840 on the metabolism of celecoxib, the sample size was determined using the conservative 90% confidence interval (CI) and 80% to 125% no-effect boundary approach described in the FDA Guidance "Clinical Drug Interaction Studies — Cytochrome P450 Enzyme- and Transporter-Mediated Drug Interactions" (2020). This guidance notes the 80 to 125% boundaries represent a very conservative standard for drugs that have wide safety "margins" and "the totality of evidence should be taken into consideration when determining the clinical impact of the DDI on the substrate drug". Therefore, if the estimated inhibition effect of ALXN1840 on celecoxib PK lies outside this no-effect boundary, this should not be interpreted as a failed study.

## 9.2. Sample Size Determination

A default of no-effect boundary (80% to 125%) approach will be employed to assess whether there is an inhibition effect on the metabolism of celecoxib in the presence of ALXN1840. For a 2-period crossover study design, assuming the true ratio of the means (celecoxib + ALXN1840 vs celecoxib alone) on the PK parameters is 1 ( $C_{max}$ ; area under the plasma concentration versus time curve from zero to infinity [AUC $\infty$ ]) and the intra-participant coefficient of variation (CV) is 0.30 (Dennison, 2018), a total sample size of 32 participants can achieve 90% power with two 1-sided tests, each with a type I error rate of 5% (two-sided type I error rate of 10%). The intraparticipant CV is estimated using residual mean-square error (MSE) term in the ANOVA model. The CV is estimated as 100% ×  $\sqrt{}$  (exp (MSE) - 1) for the log-transformed PK parameters. Assuming a 15% dropout rate, approximately 38 participants will be enrolled.

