#### **Overall Design**

This is a Phase 1, randomized, 2-period, 2-sequence, cross-over study designed to determine the effect of ALXN1840 on the metabolism of celecoxib, a sensitive CYP2C9 substrate, in healthy male and female participants. The safety and tolerability of ALXN1840 will be determined along with ALXN1840 PK in plasma as measured via total Mo with the coadministration of celecoxib.

**Disclosure Statement**: This is an open-label, 2-period, 2-sequence, cross-over study in healthy participants with randomization to 2 treatment sequences.

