at ALXN1840 concentrations  $\geq 30 \ \mu$ M. Because the maximum observed plasma total Mo concentration in the Phase 2 Study WTX101-201, conducted in patients with WD, was 20.3  $\mu$ M after repeated doing of ALXN1840 at 60 mg and then dose-escalated to 120 mg at Week 4, the observed in vitro TDI potential at ALXN1840 concentration of  $\geq 30 \ \mu$ M is not anticipated in vivo, even considering total Mo of 20.3  $\mu$ M is 100% active and free ALXN1840 (a most conservative case). Assuming 10% of the total Mo is in the form of free and active ALXN1840, which is still conservative given that most of this 10% are likely ALXN1840 degradants such as molybdate, then the highest anticipated individual free and active ALXN1840 concentration is at 2.03  $\mu$ M in patients with WD, when dosed at 120 mg daily at steady state. Overall, this, implies a negligible possibility for observing in vivo TDI with repeated daily doses of ALXN1840 at 60 mg or up to 120 mg in patients with WD.

Finally, a validated Simcyp® physiologically based pharmacokinetic model, developed using data from Study WTX101-HV-106, predicted a weak CYP2C9 inhibition potential for simulations of single dose ALXN1840 exposures at 120 or 240 mg. The predicted geometric mean of the AUC ratio of celecoxib was 1.5 for the highest simulated single dose of 240 mg ALXN1840 (Study AXP/1/B), indicating weak inhibitory potential in vivo (weak for AUC ratio of  $\geq 1.25$ - to < 2-fold), per the 2020 FDA guidance on "Clinical Drug Interaction Studies — Cytochrome P450 Enzyme- and Transporter-Mediated Drug Interactions". For the highest simulated single dose of 240 mg ALXN1840, the maximum in vivo estimated free plasma concentration available to interact with CYP2C9 is estimated at 4.1  $\mu$ M, after accounting for the formation of tetrathiomolybdate-Cu-albumin tripartite complexes (TPC), which is higher than the 2.03  $\mu$ M noted above.

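### The stated 90% power holds only a true ratio of exactly 1 in view; over the ratios the documents can support (about 1.03 to 1.14) the chance of meeting 80–125% is 79% down to 35% with 32 evaluable, and the plan shows none of this

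*Protocol*

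**What the plan says.** Protocol 9.2, repeated in SAP 4.2, sizes a two-period, two-sequence crossover "assuming the true ratio of the means (celecoxib + ALXN1840 vs celecoxib alone) on the PK parameters is 1", for Cmax and AUC∞. It takes the within-participant variability as "coefficient of variation (CV) is 0.30" and concludes that "a total sample size of 32 participants can achieve 90% power with two 1-sided tests, each with a type I error rate of 5" percent. Adding 15% dropout gives 38 enrolled. No other ratio is considered. The same section says of the boundary: "A default of no-effect boundary (80% to 125%) approach will be employed to assess whether there is an inhibition effect".

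The rationale in Protocol 2.1 expects something other than no effect to be possible. It speaks of potentially weak to moderate inhibition from one 60 mg dose. It says that a simulation model "predicted a weak CYP2C9 inhibition potential for simulations of single dose ALXN1840 exposures at 120 or 240 mg", and that "The predicted geometric mean of the AUC ratio of celecoxib was 1.5 for the highest simulated single dose of 240 mg ALXN1840". It defines weak as an AUC ratio from 1.25 to below 2. It reports no ratio for 60 mg and none for Cmax.

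Protocol 9.1 and SAP 4.1 disclaim a formal hypothesis and add that "if the estimated inhibition effect of ALXN1840 on celecoxib PK lies outside this no-effect boundary, this should not be interpreted as a failed study".

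**The concern.** For a symmetric no-effect criterion on the log scale, a true ratio of 1 gives the highest attainable probability of success. Quoting power only there tells the reader how the design performs if ALXN1840 does nothing to celecoxib. It does not say how the design performs if there is a small real effect, which the rationale treats as a live possibility. The probability falls quickly as the ratio moves away from 1, so a single figure can mislead about what 38 participants will deliver.

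What is at stake is the honesty of the planning statement and the readiness of the plan for a 90% CI that crosses 1.25. The validity of the estimate is not in question: the model, the GMR and the 90% CI are unaffected.

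**Working it through.** **Inputs.** CV 0.30, 32 evaluable and 38 enrolled, two one-sided 5% tests, bounds 0.80 and 1.25 (Protocol 9.2). AUC ratio 1.5 and maximum free concentration 4.1 µM at 240 mg; Ki 6.07 µM; single-dose 60 mg Cmax 3.92 µM; 90–95% of plasma total Mo bound; 10% free and active taken as still conservative (all Protocol 2.1).

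**Step 1: the plan's own figure.** Log-scale within-participant SD = √ln(1 + 0.30²) = √ln 1.09 = 0.2936. SE of the log ratio = 0.2936 × √(2/N), with N − 2 degrees of freedom: 0.0734 at N = 32 and 0.0673 at N = 38. Integrating over the residual variance, the probability at ratio 1 that both one-sided tests reject is 81.5% with 32, not 90%. With all 38 evaluable it is 89.2%. A single one-sided 5% test with 32 has power 90.8%, and two tests at 10% each have 91.4%, so the stated figure fits either of those but not the procedure described. The dropout step reproduces: 32/0.85 = 37.6, rounded up to 38.

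**Step 2: which ratios the documents can support at 60 mg.** None is given, so each line rests on an assumption.

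- Scaling the 240 mg result by dose (one quarter):
  - on the log scale, 1.5^(1/4) = 1.107;
  - linearly, 1 + 0.5/4 = 1.125;
  - by competitive inhibition, AUC ratio = 1/(1 − f(1 − 1/(1 + I/Ki))). Setting I = 4.1 and ratio 1.5 gives f = 0.827. With I = 4.1/4 = 1.025 µM the ratio is 1.136. (At 120 mg the same model gives 1.26, in line with the description of that dose as weak.)
- Using the free fraction and the 60 mg Cmax in the same model:
  - 10% free, I = 0.392 µM: ratio 1.053;
  - 5% free, I = 0.196 µM: ratio 1.027.

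The range is therefore about 1.03 to 1.14, for AUC only.

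**Step 3: probability that the 90% CI lies within 80–125%** (CV 0.30, same method as Step 1):

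| True ratio | 32 evaluable | 38 evaluable |
|---|---|---|
| 1.00 | 81.5% | 89.2% |
| 1.027 | 78.8% | 86.5% |
| 1.05 | 72.7% | 80.4% |
| 1.10 | 51.8% | 58.5% |
| 1.107 | 48.6% | 54.9% |
| 1.13 | 38.0% | 43.0% |
| 1.136 | 35.4% | 40.0% |

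**Step 4: splitting the gap with 32 evaluable.** From 90% to 81.5% is 8.5 points and comes from the power arithmetic. From 81.5% the assumed ratio costs a further 2.7 points at 1.027 and 46.1 points at 1.136.

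**Step 5: what the design does deliver.** The 90% CI half-width on the log scale is t × SE: 1.697 × 0.0734 = 0.1246 with 32, and 1.688 × 0.0673 = 0.1137 with 38. Exponentiated, the CI is about the GMR multiplied or divided by 1.13 or 1.12. With 32 evaluable, the probability that the upper limit is below 2.0 exceeds 99.9% for true ratios up to 1.25 and is 98.6% at 1.5.

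**The case against.** The best defence is that this is an estimation study. Protocol 9.1 and SAP 4.1 say so, appeal to the totality of evidence, and say that an effect outside the boundary does not make the study a failure. Protocol 9.4.3.1 and SAP 9.5 report the GMR with its 90% CI, and the SAP adds a forest plot. A ratio near 1 is also less odd than it looks: Protocol 2.1 describes the inhibition potential as theoretical and conservative, and Protocol 4.3 regards the microsome findings as overstating the in vivo effect. All of this stands, and it is why no resizing is called for. It does not rescue a single 90% figure that is not attained even at ratio 1, and it argues for justifying the size by precision, which the plan does not do.

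A reader might go further and infer two things that the documents do not support.

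- *That the sponsor's own simulation predicts about 1.11 to 1.14 at 60 mg, so the trial will more often than not miss the criterion.* The simulation gives a number only at 240 mg and only for AUC; the rest is scaling. The 1.136 value implies 1.025/3.92 = 26% free drug at 60 mg, well above the 5–10% that Protocol 2.1 works with. At the 10%-free ratio of 1.053 the probability is 72% with 32 and 79% with 38. Even at 1.107, 38 evaluable participants give 55%.
- *That the plan has no conclusion if the CI crosses 1.25.* It has an estimate, an interval and a stated estimation aim. What is missing is a sentence on how such an interval is read, which matters because Protocol 9.2 uses the boundary to judge whether inhibition exists.

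**Conclusion.** The concern holds in a limited form. The sample size section quotes power only at the most favourable ratio, and the quoted 90% is not delivered there (81.5% with 32 evaluable, 89.2% with 38) or at any other ratio in the supportable range. Across about 1.03 to 1.14 the probability of meeting 80–125% runs from 79% to 35% with 32 evaluable, and from 87% to 40% with 38.

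These figures assume a CV of 0.30. With 32 evaluable at ratio 1, a CV of 0.25 would give 94% and 0.35 would give 64%. The ratios rest on the scaling and free-fraction assumptions above and do not cover Cmax. The documents do not say where in the range the truth lies, so neither end should be presented as the sponsor's prediction. The planning statement needs correcting; the design and the analysis model do not.

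**What to change.** Keep 38 participants.

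1. In Protocol 9.2 and SAP 4.2, replace the single 90% figure with the probability of meeting 80–125% at ratios 1.00, 1.05, 1.10 and 1.13: 81.5%, 72.7%, 51.8% and 38.0% with 32 evaluable; 89.2%, 80.4%, 58.5% and 43.0% with 38. Do not state that the simulation points to the upper end.
2. In the same sections, justify the size by precision: an expected 90% CI of about the GMR multiplied or divided by 1.13 (32 evaluable) or 1.12 (38).
3. Optionally, in SAP 4.1 and 9.5, state how the celecoxib AUC interval will be read:
   - within 0.80–1.25: no effect;
   - upper limit above 1.25 but below 2.0: no effect not shown, and a 2-fold or greater increase excluded;
   - upper limit 2.0 or more: a 2-fold increase not excluded;
   - lower limit below 0.80: reported separately and not as inhibition.

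   This should be presented as a new reading rule. Protocol 2.1 classifies by the AUC ratio itself, not by a confidence limit.

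The cost is wording in the two documents and a less favourable stated power. No participants, samples or analyses are added.
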